9.2. Setting

The study will be performed in approximately 6 Colombian Health Provider Institution (IPS, in its Spanish acronym) whose population includes patients with ATTR-CM diagnosis in the period established. These sites will be in four Colombian cities (Bogotá, Medellin, Cali, and Barranquilla) which have a cardiologist with experience in diagnostic and management of ATTR-CM. The patients can be recruited from the same site or other healthcare institutions, which the site affiliated to the study can invite to participate. In this last scenario, the patients will maintain the clinical care of the original institution, but the information of the study will be collected in the sites affiliated to the study or by their healthcare professionals through virtual interview.

Tafamidis was approved in July 2022 by INVIMA in the treatment of ATTR-CM (14), thus, the patients with diagnosis of ATTR-CM and treated with tafamidis between August 2022 to August 2023 will be invited to participate in the study. At this time, the number of patients expected to participate will be less than 50 patients considering the number of patients diagnosed with ATTR-CM. This cohort study its representative to patients in Colombia without requiring sampling method, considering the estimated number of patients diagnosed with this disease under treatment with tafamidis.

The follow-up period is 24 months since index date with measurement every three months \pm 15 days. During this period quality of life, hospitalization frequency, and death will be measured. The endpoint of the study will be death. Additionally, adherence will be measured. For the cardiovascular functionality, it will be abstracted from the medical records 6MWT and scintigraphy during the time of study.

The activities will be included in the following table.

PFIZER CONFIDENTIAL

CT24-WI-GL02-RF01 6.0 Non-Interventional Study Protocol Template For Primary Data Collection Study 01-

Aug-2023

Page 22 of 57

**CLINICAL AND MEDICAL CONTROLLED DOCUMENT (CMCD)
REQUIRED FORM/TEMPLATE**

Identifier	Version	Title	Effective Date
CT24-WI-GL02-RF01	6.0	NON-INTERVENTIONAL STUDY PROTOCOL TEMPLATE FOR PRIMARY DATA COLLECTION STUDY	01-Aug-2023

Table 1 List of activities

Visit Identifier	Screening	Month ± 15 days										End of Observation
		-12	0	3	6	9	12	15	18	21	24	
Visit Window												
Informed consent	X											
Medical history	X											
Demographic		X										
Clinical variable		X										
Previous treatment		X										
KQCC -HRQoL		X	X	X	X	X	X	X	X	X	X	
Assessments hospitalization		X	X	X	X	X	X	X	X	X	X	
Adherence			X	X	X	X	X	X	X	X	X	
Concomitant treatment(s)			X	X	X	X	X	X	X	X	X	
6MWT*												
Scintigraphy*												

* It will be collected according to the medical criteria, considering that the physician may choose to perform a different test

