9. RESEARCH METHODS

9.1. Study design

The study will be a non-interventional, descriptive, and longitudinal prospective study with primary data collection that involves sites/investigators. The patients must be diagnosed before enrollment with ATTR-CM and prescribed with tafamidis following indications approved by National Institute for Drug and Food Vigilance (INVIMA) in Colombia. The patients will be followed up from the index date until patient i) have deceased, ii) have decided to withdraw from the study, iii) have terminated of treatment, iv) have been lost to follow up, or, v) finalize the 24 months of following up, the event that happens first. The index date will be defined as the date for the first prescription of tafamidis.

The patients that were prescribed with tafamidis before August of 2023 will be recruited. In the cases where the patients were prescribed before starting the study, all previous information will be collected from the data provided by the patients. The quality of life will be evaluated when the patient accepts to participate and signs the informed consent.

Quality of life, adherence, concomitant treatment, hospitalization for any causes, cardiovascular functionality will be measured 24 months after the prescription of tafamidis. Twelve months before the index date, treatments, and frequency of hospitalization for any causes will be measured (Table 1).

There will be two sources of information. Clinical and demographic information and death at the baseline will be abstracted from the medical record while the data related to hospitalizations, cardiovascular functionality, quality of life will be collected directly from the patients using validated questionnaires and structured interviews. Thus, in this case the report form (CRF) will serve as a source document.

In patients who have been prescribed with tafamidis more than 1 month and have not received the drug by the HMO yet, the first time of administration of tafamidis will be considered in the analysis. It will be considered as limitation of access. Any delay of supply for treatment will be considered limitation of access which will be assessed during the follow-up.

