The scale of quality of life named Kansas City Cardiomyopathy Questionnaire (KCCQ) (12) will be used after the acceptance to participate in the study by the patients with the signing of informed consent. In the statistical analysis will be considered the date to start tafamidis, the date of prescription of tafamidis and the time to start the measurement of QoL.

Data collection will be conducted with a CRF. This will be validated by two research centers to ensure feasibility of data collection, availability of the data as well as source documents and accurate definition of the study variables. The research staff at the participating centers will be trained in data extraction and completion of CRF.

The patients will be reached out to every three months±15 days through a phone call by a healthcare professional of the site. During this interview, the professional will perform a

PFIZER CONFIDENTIAL

CT24-WI-GL02-RF01 6.0 Non-Interventional Study Protocol Template For Primary Data Collection Study 01-

Aug-2023

Page 21 of 57

**CLINICAL AND MEDICAL CONTROLLED DOCUMENT (CMCD)
REQUIRED FORM/TEMPLATE**

Identifier	Version	Title	Effective Date
CT24-WI-GL02-RF01	6.0	NON-INTERVENTIONAL STUDY PROTOCOL TEMPLATE FOR PRIMARY DATA COLLECTION STUDY	01-Aug-2023

standardized interview with structured questionnaires to guarantee that the data collection process will be harmonized among patients. The interview could be in the site, if the patient received clinical care in there or she decided to move to it. Both collection data are completely accepted in the study.

The 6 min walk test (6MWT) and scintigraphy will be conducted based on the decision of cardiologist or responsible physician based on the guideline of the institution or medical practice. This study does not suggest these tests or is limited to them. They will be abstracted from medical records of patients who had measured them (13).

All assessments described in this protocol will be performed as part of normal clinical practice or standard practice guidelines for the patient population and healthcare provider specialty in Colombia where this noninterventional study is being conducted.

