9.2.1. Inclusion criteria

Patients must meet all of the following inclusion criteria to be eligible for inclusion in the study:

- Patient older than 18 years
- Spanish speaking patients
- Diagnosis of ATTR-CM confirmed by a Cardiologist
- Prescribed with tafamidis
- Evidence of a personally signed and dated informed consent document indicating that the patient (or a legally acceptable representative) has been informed of all pertinent aspects of the study.

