9.7.3. Population Analysis

9.7.3.1. Total population

The analyses will be conducted for all the eligible patients.

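### Section 9.2 invites patients already treated with tafamidis, while 9.1 and 9.2.1 require only a prescription; read literally, 9.2 cuts off late first supply and biases the access result short

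*Protocol*

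**What the plan says.** The protocol describes who enters the study in three places.

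- Section 9.2 (Setting): "the patients with diagnosis of ATTR-CM and treated with tafamidis between August 2022 to August 2023 will be invited to participate".
- Section 9.1 (Study design): "The patients that were prescribed with tafamidis before August of 2023 will be recruited". This has an upper date but no lower one, and it does not require a dose.
- Section 9.2.1 (Inclusion criteria): "Prescribed with tafamidis", with no date and no dose required.

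Section 9.1 also plans for patients who are waiting for the drug. "In patients who have been prescribed with tafamidis more than 1 month and have not received the drug by the HMO yet", it says, "the first time of administration of tafamidis will be considered in the analysis. It will be considered as limitation of access". Follow-up is anchored on the prescription: "The index date will be defined as the date for the first prescription of tafamidis". Table 2 records the prescription date and the first-administration date as separate variables.

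On analysis, section 9.7.3.1 says "The analyses will be conducted for all the eligible patients". Section 9.1 adds, with quality of life as the measurement meant: "In the statistical analysis will be considered the date to start tafamidis, the date of prescription of tafamidis and the time to start the measurement". Section 9.7.3.2 lists subgroups for any delay of supply and for time on tafamidis before enrollment. Describing access barriers is a secondary objective (section 8).

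**The concern.** Treated and prescribed are not interchangeable here, because the protocol itself separates them. A patient prescribed in June 2023 and first supplied in October 2023 is outside the 9.2 invitation but meets 9.1 and 9.2.1. About six sites would apply these sections to about 50 patients, so sites reading different sections would recruit different cohorts.

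Under 9.2, being supplied by the closing date is a condition of entry, while delay in supply is one of the things the access objective describes. That is right truncation of the time to first supply. No later analysis can recover patients who were never invited.

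Under 9.1 and 9.2.1 there is a lesser problem. The analysis population carries no dosing condition, so a never-dosed patient, or a KCCQ score taken before the first dose, could be reported as part of the impact of tafamidis use.

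**Working it through.** The protocol contains no figure to reproduce on this point. The check is date arithmetic on its own dates, followed by an illustration with assumed delays.

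**Inputs from the protocol.** Treatment window August 2022 to August 2023 (9.2). Prescription before August 2023 (9.1). Start of data collection 15 November 2023 (section 6). First KCCQ after consent (9.1). About 50 patients (9.5; 9.2 says fewer than 50).

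**Assumption on dates.** The 9.2 window closes on 31 August 2023.

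**Step 1: longest first-supply delay that 9.2 can keep** = closing date − prescription date. **Shortest delay that leaves a patient undosed at the earliest possible first KCCQ** = 15 November 2023 − prescription date.

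| Prescribed | Longest delay kept under 9.2 (days) | Shortest delay to be undosed at first KCCQ (days) |
|---|---|---|
| 1 Aug 2022 | 395 | 471 |
| 1 Feb 2023 | 211 | 287 |
| 1 Jul 2023 | 61 | 137 |
| 31 Jul 2023 | 31 | 107 |

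If the window is read as closing on 1 August 2023, the middle column runs from 365 days down to 1 day. Never-supplied patients are excluded under either date.

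**Step 2: how many 9.2 would drop.** Assume prescriptions uniform over 12 months from August 2022, an exponential delay with mean m months, and closure at month 13. The excluded share is (m/12) × [exp(−1/m) − exp(−13/m)].

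- m = 2: (2/12) × (0.6065 − 0.0015) = 0.101, or 5.0 of 50. The mean delay among those kept is about 1.67 months instead of 2.0.
- m = 3: (3/12) × (0.7165 − 0.0131) = 0.176, or 8.8 of 50. The mean among those kept is about 2.19 months instead of 3.0, and about 41% of delays over 3 months are lost.

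**Step 3: undosed at the earliest first KCCQ under the 9.1 rule.** Same assumptions, with 15 November 2023 at month 15.5. The share is (m/12) × [exp(−3.5/m) − exp(−15.5/m)].

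- m = 2: (2/12) × (0.1738 − 0.0004) = 0.029, or 1.4 of 50.
- m = 3: (3/12) × (0.3114 − 0.0057) = 0.076, or 3.8 of 50.

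**Step 4: effect on the reported KCCQ change.** Treat every such patient as undosed throughout and unchanged, so that the reported change is the true change × (1 − undosed share). For 5 points, the smallest change that section 9.3.1 calls clinically important, 3% undosed gives 5 × 0.97 = 4.85 and 8% gives 5 × 0.92 = 4.6.

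**The case against.** The strongest reply is that *treated* in 9.2 is a slip. The formal criteria in 9.2.1 say prescribed, 9.1 says prescribed and writes in patients who are still waiting, and the index date is the prescription. On that reading the intended rule is clear and this is a one-word correction. It is the likelier intention, and it supports the fix. The conflict remains, because 9.2 is where the protocol says who is to be invited.

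Three stronger readings are tempting, and the text does not support them.

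- *That 9.1 admits anyone ever prescribed the drug.* It does not: it stops at prescriptions before August 2023. Only 9.2.1 has no date.
- *That 9.2 removes all the worst access problems.* It does not. A patient prescribed early with a delay of many months stays in if dosed before the window closes. Section 9.1 also counts any later delay of supply as an access limitation, to be assessed during follow-up, and Table 2 records it as yes or no with a cause, so resupply delays are captured under either rule. The bias is confined to time to first supply. The means above illustrate it; section 9.7.5.1 plans medians and interquartile ranges for continuous variables.
- *That the prescribed rule seriously dilutes the quality-of-life result.* Under 9.1 a patient must have waited at least 107 days to be undosed at the first KCCQ. One who starts later supplies a genuine pre-treatment score, which section 9.9 suggests will be hard to obtain. The protocol also promises to consider the start date and lists a delay subgroup. Finer handling may properly sit in the SAP, which is not at hand.

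**Conclusion.** The entry conditions in 9.2 and in 9.1 and 9.2.1 conflict and need to be reconciled. Applied literally, 9.2 truncates the time to first supply: the longest delay it can keep falls from about 395 to about 31 days across the prescription period, and never-supplied patients disappear. First-supply delay in the access objective would then be biased short. The direction follows from the protocol's own dates. The count of about 5 to 9 of 50 dropped rests on an assumed exponential delay with mean 2 to 3 months, and the true distribution is not in the document.

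The quality-of-life consequence of the prescribed rule is secondary and probably small: about 3% to 8% undosed at the earliest first KCCQ under the same assumptions, so that a 5-point change reads as about 4.85 to 4.6. Late starters counted as unchanged make this an overstatement; deterioration among undosed patients would work the other way. Under 9.2.1 taken alone, with no date limit, even a short delay could leave a patient undosed at the first KCCQ, which is a further reason to fix the window.

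**What to change.** Use one entry rule in 9.1, 9.2 and 9.2.1: first tafamidis prescription within one stated window, from August 2022 to a single cut-off date, whether or not the drug has been supplied. Replace *treated* in 9.2 accordingly.

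In 9.7.3.1, state that never-dosed patients count for the access-barrier and baseline objectives but are reported separately from the quality-of-life result. State also that KCCQ scores obtained before first administration are kept as pre-treatment baseline, neither discarded nor counted as on-treatment. Counting KCCQ only from the first administration would be the wrong remedy, because it would discard the only true pre-treatment scores.

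The cost is protocol wording and one analysis-set definition, since both dates are already collected in Table 2. The one downside is that the dosed quality-of-life set may be a few patients smaller than the enrolled set.

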6. MILESTONES

Milestone	Planned date
Completion of feasibility assessment	12 May 2023
Registration in the EU PAS register	15 October 2023
Start of data collection	15 November 2023
End of data collection	30 July 2025
Start date of data analysis	16 September 2024
Study progress report 1	30 August 2024
Interim report 1	30 July 2024
Interim report 2	15 January 2025
Final study report	15 January 2026

PFIZER CONFIDENTIAL

CT24-WI-GL02-RF01 6.0 Non-Interventional Study Protocol Template For Primary Data Collection Study 01-Aug-2023
Page 17 of 57

CLINICAL AND MEDICAL CONTROLLED DOCUMENT (CMCD) REQUIRED FORM/TEMPLATE

Identifier	Version	Title	Effective Date
CT24-WI-GL02-RF01	6.0	NON-INTERVENTIONAL STUDY PROTOCOL TEMPLATE FOR PRIMARY DATA COLLECTION STUDY	01-Aug-2023

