previously forwarded safety event reports. In the rare situation that the investigator does not become immediately aware of the occurrence of a safety event, the investigator must report the event within 24 hours after learning of it and document the time of his/her first awareness of the events.

For safety events that are considered serious or that are identified in the far-right column of the table above that are reportable to Pfizer within 24 hours of awareness, the investigator is obligated to pursue and to provide any additional information to Pfizer in accordance with this 24-hour timeframe. In addition, an investigator may be requested by Pfizer to obtain specific follow-up information in an expedited fashion. This information is more detailed than that recorded on the CRF. In general, this will include a description of the AE in sufficient detail to allow for a complete medical assessment of the case and independent determination of possible causality. Any information relevant to the event, such as concomitant medications and illnesses, must be provided. In the case of a patient death, a summary of available autopsy findings must be submitted as soon as possible to Pfizer or its designated representative.

Reporting period

For each patient, the safety event reporting period begins at the time of the patient's first dose of tafamidis or the time of the patient's informed consent if s/he is being treated with tafamidis at study start, and lasts through the end of the observation period of the study, which must include at least 28 calendar days following the last administration of a drug under study; a report must be submitted to Pfizer Safety (or its designated representative) for any of the types of safety events listed in the table above occurring during this period. If a patient was administered a drug under study on the last day of the observation period, then the reporting period should be extended for 28 calendar days following the end of observation. Most often, the date of informed consent is the same as the date of enrollment. In some situations, there may be a lag between the dates of informed consent and enrollment. In these instances, if a patient provides informed consent but is never enrolled in the study (e.g., patient changes his/her mind about participation, failed screening criteria"), the reporting period ends on the date of the decision to not enroll the patient.

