3.1 Is the study design described? (e.g., cohort, case-control, cross-sectional, other design)				9.1

¹ Date from which information on the first study is first recorded in the study dataset or, in the case of secondary use of data, the date from which data extraction starts.

² Date from which the analytical dataset is completely available.

**CLINICAL AND MEDICAL CONTROLLED DOCUMENT (CMCD)
REQUIRED FORM/TEMPLATE**

Identifier	Version	Title	Effective Date
CT24-WI-GL02-RF01	6.0	NON-INTERVENTIONAL STUDY PROTOCOL TEMPLATE FOR PRIMARY DATA COLLECTION STUDY	01-Aug-2023

Section 3: Study design	Yes	No	N/ A	Section Number
3.2 Does the protocol specify whether the study is based on primary, secondary, or combined data collection?				9.1
3.3 Does the protocol specify measures of occurrence? (e.g., rate, risk, prevalence)				
3.4 Does the protocol specify measure(s) of association? (e.g., risk, odds ratio, excess risk, rate ratio, hazard ratio, risk/rate difference, number needed to harm (NNH))				9.7.5.2
3.5 Does the protocol describe the approach for the collection and reporting of adverse events/adverse reactions? (e.g., adverse events that will not be collected in case of primary data collection)				10

Comments:

Section 4: Source and study populations	Yes	No	N/ A	Section Number
4.1 Is the source population described?				9
4.2 Is the planned study population defined in terms of:				
4.2.1 Study time period				9.2
4.2.2 Age and sex				9.2
4.2.3 Country of origin				9.2
4.2.4 Disease/indication				9.2
4.2.5 Duration of follow-up				9.2

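### Data collection closes on 30 July 2025, before the last patients' month-24 target and 28-day safety period, and sections 9.1 and 9.2 give different recruitment cut-offs

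*Protocol*

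**What the plan says.** Five statements in the protocol have to fit together.

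- **Clock.** Section 9.1: "The index date will be defined as the date for the first prescription of tafamidis". Section 9.2: "The follow-up period is 24 months since index date with measurement every three months", with a tolerance of ±15 days. Table 1 schedules the KCCQ at month 24.
- **Who is recruited.** Section 9.1: "The patients that were prescribed with tafamidis before August of 2023 will be recruited". The abstract says the same. Section 9.2 says that those "treated with tafamidis between August 2022 to August 2023 will be invited to participate in the study". The first ends with July 2023. The second runs into August 2023, and it speaks of treatment rather than prescription.
- **Close.** Section 6 puts the end of data collection at 30 July 2025. The Annex 2 checklist footnote defines that milestone as "Date from which the analytical dataset is completely available".
- **Safety.** Section 11 runs the reporting period to the end of observation, "which must include at least 28 calendar days following the last administration of a drug under study". It adds 28 days after the end of observation for a patient dosed on the last day.
- **Reports.** Section 6 dates Interim report 1 at 30 July 2024 and the start of data analysis at "16 September 2024".

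**The concern.** The primary objective is quality of life over two years, so the month-24 KCCQ completes it. If the dataset must be complete on 30 July 2025, the patients prescribed last have a shortened month-24 window or none. Section 9.7.4 rules out imputation, so a missed final score stays missing. The loss depends on calendar date and falls only on the latest-prescribed patients, in a cohort that section 9.2 expects to be under 50.

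Section 9.8 plans a consistency review with queries to sites after collection has finished. If the dataset is to be complete on 30 July 2025, the last usable contact would have to come earlier still.

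Safety is affected too. Section 11 requires all serious and non-serious adverse events on the CRF, so events in the last weeks of the reporting period would arrive after the dataset is meant to be complete.

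**Working it through.** **Inputs.** Close E = 30 July 2025 (section 6). Target T = index date + 24 months (9.1, 9.2). Visit window = T − 15 to T + 15 days (9.2). Safety period ends at T + 28 days, or at T + 15 + 28 days if observation ends on the last day of the visit window (section 11). Last index date = 31 July 2023 under 9.1, or 31 August 2023 under 9.2 if the whole month counts.

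**The plan's own date.** 30 July 2023 + 24 months = 30 July 2025. The close therefore equals the bare month-24 target of an index date one day before the 9.1 cut-off, with no room for the window or the safety period.

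**Last patient under each wording**

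| | 9.1 (index 31 July 2023) | 9.2 (index 31 August 2023) |
|---|---|---|
| Target | 31 July 2025, 1 day after E | 31 August 2025, 32 days after E |
| Window | 16 July to 15 August 2025 | 16 August to 15 September 2025 |
| Safety end, from target | 28 August 2025, 29 days after E | 28 September 2025, 60 days after E |
| Safety end, from window close | 12 September 2025, 44 days after E | 13 October 2025, 75 days after E |

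**Latest index date that still fits, working back from E**

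- Target on or before E: 30 July 2023.
- Whole window on or before E: 30 July − 15 days = 15 July 2025, so 15 July 2023.
- Window opens on or before E: 30 July + 15 days = 14 August 2025, so 14 August 2023. From 15 August 2023 no in-window visit is possible.
- 28 days from target on or before E: 30 July − 28 days = 2 July 2025, so 2 July 2023.

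**Number of patients.** Assume 50 patients with index dates spread evenly from 1 August 2022. The protocol gives no distribution. The 9.1 range is then 365 days and the 9.2 range 396 days.

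- 9.1, window cut short (16 to 31 July): 16/365 = 4.4%, about 2 patients. None loses the visit outright.
- 9.2, target after the close (31 July to 31 August): 32/396 = 8.1%, about 4 patients. Whole window lost (15 to 31 August): 17/396 = 4.3%, about 2 patients.
- Safety period past the close (index from 3 July), if all are still on drug at month 24: 29/365 = 7.9%, about 4 patients under 9.1; 60/396 = 15.2%, about 8 under 9.2.

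**Report order.** 30 July 2024 to 16 September 2024 is 48 days, with the report first.

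**Room before the final report (15 January 2026).** From 12 September 2025, 125 days; from 13 October 2025, 94 days.

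**The case against.** The strongest reply is that the visit problem is small. The abstract and 9.1 agree on prescriptions before August 2023. On that wording the last target misses by one day, its window opens on 16 July 2025, and every month-24 visit can still be held. A visit becomes impossible only if 9.2 is read to include the second half of August. Month 24 is also one point in a quarterly series. All of this stands, and it limits the size of the point. It does not remove it: 9.2 does say August 2023, the tolerance is shortened even under 9.1, and the safety period overruns under both wordings.

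It can also be said that 12 September and 13 October 2025 are upper bounds, because they assume that observation ends on the last day of the visit window. That is correct. Counted from the target, the dates are 28 August and 28 September 2025, both still after the close.

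A reader might go further and infer that every patient with delayed supply is cut off months before month 24. The documents do not support this. Section 9.1 says only that first administration will be considered in the analysis and treated as an access limitation. The index date and the 24 months stay tied to the prescription, and no passage restarts the clock. Even with a restart, a patient prescribed on 1 August 2022 and first dosed on 15 September 2022 would reach month 24 on 15 September 2024, 318 days before the close.

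What remains is narrower. A patient still unsupplied when data collection starts on "15 November 2023" could have at most 20 months and 15 days (about 20.5 months) on drug by 30 July 2025. Section 9.1 provides for unsupplied patients, whereas 9.2's requirement of treatment by August 2023 appears to exclude anyone still without drug at that date.

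**Conclusion.** The milestones cannot deliver the stated follow-up and safety reporting for all eligible patients. Data collection ends 1 day (9.1) or 32 days (9.2, all of August included) before the last month-24 target. It ends 29 or 60 days before the last 28-day safety period closes, counted from the target. Outright loss of the final KCCQ is confined to index dates of 15 to 31 August 2023, about 2 of 50 patients if prescriptions are evenly spread. Under 9.1 no visit is necessarily lost.

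The dates follow directly from the protocol. The patient counts rest on the even-spread assumption, on 1 August 2022 as the first index date and on a cohort of 50. The safety overrun concerns only patients still on drug at month 24. Interim report 1 precedes the stated start of analysis. The protocol does not say what that report contains, so the order needs correcting or explaining.

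**What to change.** 1. State one cut-off, expressed as a prescription date, in the abstract, 9.1 and 9.2.
2. Move the end of data collection past the last month-24 window and the 28-day safety period: no earlier than 12 September 2025 for a 31 July 2023 cut-off, or 13 October 2025 for 31 August 2023, plus time for cleaning and the section 9.8 queries.
3. Put Interim report 1 after the start of data analysis, or bring that start forward.
4. Reconcile 9.1's sentence on patients not yet supplied with 9.2's treated-by-August-2023 wording, and state that the 24 months run from prescription for these patients too, if that is the intention.

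The cost is a few sentences and milestone entries. No sample size or analysis method changes. The final report can stay at 15 January 2026, with 125 or 94 days left before cleaning is deducted.
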